1.1.3. Other Efficacy Objectives

Other Efficacy Objectives	Endpoints

Other Efficacy Objectives	Endpoints

Other Efficacy Objectives	Endpoints

[figure not shown]
1.2. Study Design

1.2.1. Overall Study Design

This study is a Phase 2 randomized, double-blind, placebo-controlled, parallel-group, multicenter study to evaluate the efficacy and safety of vibegron in women with IBS-D or IBS-M. Subjects who meet all eligibility criteria will be randomized in a 1:1 ratio to receive either vibegron 75 mg or matched placebo. Approximately 200 subjects will be enrolled at approximately 40 sites in the US to achieve approximately 180 evaluable subjects (90 per treatment group).

The study consists of a Screening Period (1 to 5 weeks), a single-blind Placebo Run-in Period (2 weeks), a randomized, Double-blind Treatment Period (12 weeks), and a Safety Follow-up Period (2 weeks). Subjects will have a Safety Follow-up phone call approximately 14 days after the subject's last dose of study drug (i.e., at Week 14 for subjects who complete the Week 12 Visit, or approximately 2 weeks after the last dose of study drug for subjects who discontinue treatment early). The study schema is shown in [Figure 1](#).

Figure 1: Study Schema

The Week 14 Safety Follow-up telephone call should occur 7 to 14 days after the last dose of study drug (includes window of – 7 days) only for randomized subjects who complete Week 12 or withdraw from the study early.

Refer to Section 1.3 of the protocol for a detailed time and events schedule.

1.2.2. Randomization and Blinding

Randomization will occur centrally using an interactive voice or web response system (IxRS) using central, stratified block randomization. Randomization will be stratified based on the following stratification factors:

- Baseline abdominal pain intensity score (<6 vs ≥ 6) on a 0 to 10 numeric rating scale [NRS], and
- IBS subtype (IBS-D vs IBS-M)

For this study a double-blind/masking technique will be used: vibegron and its matching placebo will be packaged identically so that treatment blind/masking is maintained. The subject, the Investigator, and Sponsor personnel or delegate(s) who are involved in the treatment or clinical evaluation of the subjects will not be aware of the treatment group assignments.

1.2.3. Statistical Hypotheses

The primary objective will be to estimate the treatment effect of vibegron relative to placebo with respect to improvement in IBS-related abdominal pain in IBS-D subjects. There is no formal statistical hypothesis. Nominal p-values from comparisons to placebo may be provided

for descriptive purposes. An improvement in the primary endpoint is defined as a subject who experiences a decrease in the weekly average of “worst abdominal pain in the past 24 hours” scores of at least 30% compared with the baseline weekly average. Sample Size Justification

Approximately 200 subjects will be randomized in a 1:1 ratio to receive one of the following study treatments:

- Vibegron 75 mg tablet (N = 100)
- Matching placebo tablet (N = 100)

At most, 50% of randomized subjects (approximately 100 subjects total [approximately 50 per treatment arm]) will have IBS-M; at least 50% of randomized subjects (approximately 100 subjects total [approximately 50 per treatment arm]) will have IBS-D, and the IBS-D subgroup will be used for the primary endpoint analysis. Assuming a total of 10% of subjects will discontinue prior to Week 12 (for any reason), there will be a minimum of approximately 90 evaluable IBS-D subjects (approximately 45 in the vibegron arm and approximately 45 in the placebo arm) at the end of Week 12. The study has approximately 60% power to detect a between-group treatment difference of 20% in proportion of abdominal pain responders at a 2 - sided test at the $\alpha = 0.10$ level assuming a responder rate of 51% versus 31% for vibegron and placebo, respectively. The assumptions were based on results from a solabegron study female subgroup analysis [Kelleher, 2008].

2. PLANNED ANALYSES

2.1. Interim Analysis

2.2. Final Analysis

██████████ will perform the production and quality control of all tables, figures and listings on behalf of Urovant Sciences, Inc.

Statistical programming will start after data have been collected and are available in the database. Blinded dry runs using dummy treatment code will be performed prior to database lock and unblinding to ensure programming displays and algorithms are developed as planned.

3. ANALYSIS POPULATION

3.1. Analysis Sets

3.1.1. Screened Set

The Screened Set consists of all subjects who are screened for the study. This population is used primarily for subject accounting purposes and will generally not be used for summary or analysis.

3.1.2. Placebo Run-in Set

The Placebo Run-in Set consists of all subjects who entered the single-blind placebo Run-in period of the study. Subjects will be considered Run-in failures if they enter the Run-in period but are not randomized to receive double-blind medication.

3.1.3. Randomized Set

The Randomized Set consists of all subjects who are randomized to receive any double-blind study medication regardless of whether they took a dose.

3.1.4. Safety Analysis Set

The Safety Analysis Set (SAF) consists of all subjects who receive at least one dose of double-blind study medication. Subjects will be classified according to the treatment they actually received.

3.1.5. Full Analysis Set

The Full Analysis Set (FAS) consists of all randomized subjects who took at least one dose of double-blind study medication and had at least one evaluable post-baseline weekly API score (i.e., where evaluable is considered minimum of 5 diary entries in a week). Subjects will be analyzed according to their randomized treatment, irrespective of whether or not they have prematurely discontinued, according to the Intent-to-Treat principle. The Full Analysis Set for IBS-D (FAS-D) and Full Analysis Set for IBS-M (FAS-M) are each a subset of FAS and consists of IBS-D and IBS-M subjects, respectively, based on the randomization strata. In general, the efficacy endpoints will be summarized using all three populations: FAS, FAS-D

and FAS-M. However, the FAS-D will serve as the primary population for the primary analysis of efficacy data in this study.

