9.3. Populations for Analyses

The analysis populations will consist of subjects as defined below:

- The Screened Analysis Set includes all subjects who are screened for the study. This population is used primarily for subject accounting purposes and will generally not be used for summary or analysis.
- The Randomized Set includes all subjects who are randomized to receive study drug regardless of whether they take a dose.
- The Safety Analysis Set includes all subjects who receive at least one dose of study drug. Subjects will be classified according to the treatment they actually receive.
- The Full Analysis Set (FAS) includes all randomized IBS-D and IBS-M subjects who took at least one dose of double-blind study drug and had a baseline diary assessment and at least 1 post-randomization diary entry. Subjects will be analyzed according to randomized treatment, irrespective of whether or not they have prematurely discontinued, according to the Intent -to-Treat principle. The Full Analysis Set for IBS-D (FAS-D) and Full Analysis Set for IBS-M (FAS-M) are each a subset of FAS and consists of IBS-D and IBS-M subjects, respectively. The FAS-D will serve as the primary population for the primary analysis of efficacy data in this study.
- The Per-Protocol Set for IBS-D excludes subjects from the FAS-D due to important deviations from the protocol that may substantially affect the result of the primary efficacy endpoint (ie, Major Protocol Deviations associated with efficacy). The Per -Protocol Set will serve as the supportive population for the analysis of efficacy data in this study. Other Per-Protocol Sets may be defined.

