4.3.1.1. API Weekly Responder

To derive API Weekly Responder during various week intervals, the initial two steps should be followed to derive (1) Weekly average worst abdominal pain (WAP) score; (2) Weekly Responder status by week

Step 1:

- Weekly average is defined as the sum of WAP scores on the NRS (0-10) in the 7 days immediately prior to baseline visit (Day 1) or each of post-baseline Weeks (Week 1-Week 12), divided by the number of days with non-missing pain diary entries during the 7 days. Weekly average will be set missing if there are more than 2 missed diary days over the past 7 days.
- API Weekly Responder with $\geq 30\%$ improvement at each week (i.e., Week 1, Week 2, Week 3, ..., Week 12) is defined as a subject who experiences a decrease in the weekly average of WAP score of at least 30% compared with the baseline weekly average. To qualify as a responder for the specific week, a subject must have at least 5 days of non-missing pain diary entries during the week (i.e., ≥ 5 of 7 days). A Subject will be assigned as non-responder for the specific week if the weekly average is missing.

Similarly, the API Weekly Responder will be further derived based on more stringent measures of weekly reduction as below:

- API Weekly Responder with $\geq 40\%$ improvement at each week (i.e., Week 1, Week 2, Week 3, ..., Week 12) is defined as a subject who experiences a decrease in the weekly

average of WAP score of at least 40% compared with the baseline weekly average. To qualify as a responder for the specific week, a subject must have at least of 5 days of non-missing pain diary entries during the week (i.e., ≥ 5 of 7 days).

- API Weekly Responder with $\geq 50\%$ improvement at each week (i.e., Week 1, Week 2, Week 3, ..., Week 12) is defined as a subject who experiences a decrease in the weekly average of WAP score of at least 50% compared with the baseline weekly average. To qualify as a responder for the specific week, a subject must have at least of 5 days of non-missing pain diary entries during the week (i.e., ≥ 5 of 7 days).

Step 2:

Then API Weekly Responder will be derived during different treatment intervals using primary criteria as an example below:

API Weekly responder with $\geq 30\%$ improvement over 12 weeks (i.e., from randomization through to Week 12) - primary efficacy endpoint

- To qualify as an overall API Weekly Responder from randomization through to Week 12 (Weeks 1-12), a subject must satisfy the following criteria:

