 - Must meet the API Weekly Response criteria $\geq 30\%$ improvement on $\geq 50\%$ of weeks, i.e., success on 6 or more weeks during the past 12 weeks
 - Must have had ≥ 60 diary days over the past 12 weeks

API Weekly responder from randomization through to Week 2 (Weeks 1-2)

- To qualify as an API Weekly Responder from randomization through to Week 2, a subject must satisfy the following criteria:
 - Must meet the API Weekly Response criteria on more than 50% of weeks, i.e., success on 1 or 2 weeks during past 2 weeks
 - Must have had ≥ 10 diary days over the past 2 weeks

API Weekly Responder from randomization through to Week 4 (Weeks 1-4)

- To qualify as an API Weekly Responder over 4-week interval, a subject must satisfy the following criteria:
 - Must meet the API Weekly Response criteria on more than 50% of weeks, i.e., success on 2 or more weeks during past 4 weeks
 - Must have had ≥ 20 diary days over the past 4 weeks

API Weekly Responder from randomization through to Week 8 (Weeks 1-8)

- To qualify as an API Weekly Responder over 8-week interval, a subject must satisfy the following criteria:
 - Must meet the API Weekly Response criteria on more than 50% of weeks, i.e., success on 4 or more weeks during past 8 weeks
 - Must have had ≥ 40 diary days over the past 8 weeks

The secondary efficacy endpoints of Weekly API Responder with either $\geq 40\%$ or $\geq 50\%$ improvement will be classified using the same rules above.

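### The SAP's Full Analysis Set drops randomised, dosed women who never complete a five-entry diary week; all are certain non-responders, and the protocol defines the set differently

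*SAP*

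**What the plan says.** Protocol 9.3 admits a randomised, dosed woman to the Full Analysis Set (FAS) if she "had a baseline diary assessment and at least 1 post-randomization diary entry". SAP 3.1.5 replaces the diary part of that rule: she must have "had at least one evaluable post-baseline weekly API score (i.e., where evaluable is considered minimum of 5 diary entries in a week".

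The same SAP paragraph says that subjects are analysed as randomised, "irrespective of whether or not they have prematurely discontinued, according to the Intent-to-Treat principle", and that "the FAS-D will serve as the primary population for the primary analysis of efficacy data in this study". FAS-D, the IBS-D subset, inherits the five-entry condition.

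SAP 4.3.1.1 already deals with incomplete diaries inside the endpoint:
- Weekly average: "Weekly average will be set missing if there are more than 2 missed diary days over the past 7 days".
- Weekly status: "A Subject will be assigned as non-responder for the specific week if the weekly average is missing".
- Overall responder over 12 weeks: "success on 6 or more weeks during the past 12 weeks", and "Must have had ≥ 60 diary days over the past 12 weeks".

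SAP 4.2.3 relies on these rules when it states that responder status needs no imputation.

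**The concern.** The endpoint definition turns diary gaps into non-response, but the population definition removes the women with the largest gaps before the endpoint is applied. Inclusion then depends on something that happens after randomisation, and everyone it removes has the same outcome. That does not fit the Intent-to-Treat principle claimed in the same paragraph.

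The women most exposed are those who stop in the first days. Under Protocol 7.2, stopping study drug means leaving the study, and Week 1 is Days 1 to 7. A woman who leaves before her fifth Week 1 entry can never qualify. Adverse events and lack of efficacy are among the listed reasons for stopping (Protocol 7.1), and either may differ between arms. If so, the responder-rate difference is biased in favour of the arm that loses more women.

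The secondary responder analyses rest on the same set. GIS is collected at visits, and SAP 4.3.1.2 already counts a missing response as non-response. Even so, a woman with a valid Week 12 GIS and a poor diary would be left out of the GIS analysis.

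**Working it through.** **1. The plan's own figure.** Protocol 9.2 states about 60% power for 51% against 31% responders, 45 evaluable IBS-D women per arm, two-sided alpha 0.10. With the pooled normal approximation:
- Null SE = √(2 × 0.41 × 0.59 / 45) = 0.1037.
- Alternative SE = √((0.51 × 0.49 + 0.31 × 0.69) / 45) = 0.1015.
- Power = Φ((0.20 − 1.645 × 0.1037) / 0.1015) = 61.4%, which reproduces the stated value.

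**2. Can an excluded woman be a responder?** She has at most 4 entries in every week.
- Every weekly average is missing, so every week counts as non-response: 0 responder weeks against 6 needed.
- Her diary days total at most 4 × 12 = 48 against 60 needed.

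She fails both criteria, so she is a non-responder with certainty.

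**3. Effect on a rate.** If a share e of an arm is excluded and all of them are non-responders, the FAS-D rate is the all-dosed rate divided by (1 − e). The documents do not give e. The assumed range is 0 to 10% per arm, where 10% is the total discontinuation planned in Protocol 9.2.

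| Excluded, vibegron / placebo | All-dosed rates | FAS-D rates | Difference |
|---|---|---|---|
| 5% / 5% | 51% vs 31% | 53.7% vs 32.6% | 21.1 points (20 true) |
| 10% / 10% | 51% vs 31% | 56.7% vs 34.4% | 22.2 points (20 true) |
| 10% / 0% | 31% vs 31% | 34.4% vs 31.0% | 3.4 points (0 true) |

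**4. Effect on the reported result.** Take the planned 50 IBS-D women per arm and whole-number responder counts near the planned rates: 25 on vibegron, 16 on placebo. The SAP 6.1.1 formula is applied with one stratum, so RD = 25/(50 − k_v) − 16/(50 − k_p), with the unpooled variance and z = 1.645.

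With all women kept, the variance is 0.50 × 0.50/50 + 0.32 × 0.68/50 = 0.00935 and the SE is 0.0967.

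| k_v, k_p | RD (points) | 90% CI | Nominal p |
|---|---|---|---|
| 0, 0 | 18.0 | 2.1 to 33.9 | 0.063 |
| 1, 1 | 18.4 | 2.3 to 34.5 | 0.061 |
| 3, 1 | 20.5 | 4.3 to 36.8 | 0.038 |
| 5, 1 | 22.9 | 6.5 to 39.3 | 0.022 |
| 5, 5 | 20.0 | 3.1 to 36.9 | 0.052 |
| 1, 5 | 15.5 | −1.1 to 32.1 | 0.126 |

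**5. Does anything planned put these women back?** The sensitivity analyses in SAP 6.1.2 are PPS-D (drawn from FAS-D), logistic regression on the FAS, a rescue-medication rule, and actual strata. None restores them. The legible part of SAP Section 9 does not list the FAS definition as a change from the protocol.

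**The case against.** The strongest reply has five parts.

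- **The conflict is narrower than it looks.** The protocol's FAS also drops dosed women with no post-randomisation entry, who are equally certain non-responders. The direct conflict concerns women with at least one entry but no five-entry week. The SAP also omits the protocol's baseline-diary condition, a difference in the opposite direction. This stands, and it means that the preferred fix goes beyond the protocol and must be declared.
- **The rule selects on diary completeness, not on pain.** This is true, and a woman with five entries in Week 1 who then stops is kept. But everyone excluded is a non-responder by the SAP's own definition, so the effect is the same.
- **The numbers may be small.** The two-week run-in, the diary training and the baseline pain criterion, which draws on five diary days, all favour women who can keep a diary. Five exclusions in one arm would use up that arm's whole 10% allowance. With 2 against 1 excluded, the estimate moves only from 18.0 to 25/48 − 16/49 = 19.4 points, well inside a 90% CI half-width of about 16 points. A woman with a Week 12 GIS (window from Day 71) and no five-entry week would be rare. All this limits the likely size, but the documents give no count that would settle it.
- **The exclusions are reported.** SAP 5.1 summarises reasons for exclusion by arm, so a reader could add the women back. That helps transparency but leaves the primary estimate and interval as they are.
- **Everything is descriptive.** There is no formal hypothesis. But SAP 1.2.3 makes estimating the treatment effect the primary objective, and a distorted estimate bears directly on that.

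**Conclusion.** The concern holds. The SAP's primary population removes only certain non-responders, departs from the protocol's definition without a legible declaration, and is not offset by any planned sensitivity analysis.

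With equal exclusion and no true effect there is no bias in the difference. With equal exclusion of 5 to 10%, a true 20-point difference appears as 21.1 to 22.2. With unequal exclusion the bias can run either way: from 15.5 to 22.9 points around a value of 18.0 when 1 against 5, or 5 against 1, of 50 women are dropped.

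These sizes rest on assumed exclusion counts, illustrative responder counts and a single stratum. The conclusion that every excluded woman is a non-responder rests on the SAP's rules alone.

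**What to change.** In SAP 3.1.5, define the FAS, and with it FAS-D and FAS-M, as all randomised women who took double-blind drug, with no post-baseline diary condition. State that a woman without an evaluable week is a non-responder, as 4.3.1.1 already implies. Because this goes further than Protocol 9.3, record it in SAP Section 9. The present five-entry set can be kept as a supportive analysis.

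The minimum alternative is to restore the protocol's definition. That removes the contradiction but still leaves out women with no post-randomisation entry.

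Make the change before unblinding. It costs SAP wording and a Section 9 entry and needs no new data. Responder rates will be slightly lower in any arm that has such women. The change-from-baseline analysis of weekly average pain is not affected by these women, who have no post-baseline weekly average to contribute.

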3.1.6. Per-Protocol Set

The Per-Protocol Set for IBS-D (PPS-D) excludes subjects from the FAS-D due to important deviations from the protocol that may substantially affect the result of the primary efficacy endpoint. This Per -Protocol Set will serve as the supportive population for the analysis of efficacy data in this study. Other Per Protocol Sets may be defined. The final determination on major protocol deviations, and thereby the composition of the Per-Protocol Sets, will be made prior to the unblinding of the database and will be documented.

3.2. Violations and Deviation

Subjects who do not meet eligibility criteria but were still randomized will be analyzed according to the analysis sets described in [Section 3.1](#).

3.2.1. Protocol Deviations

The final list of major protocol deviations will be finalized and documented prior to database lock except for the deviation category of wrong treatment which will be confirmed upon study unblinding. Only major (i.e., significant per the protocol deviation plan) protocol deviations will be summarized and listed in the Clinical Study Report (CSR). Major deviations will be those which are considered to potentially impact upon the interpretation of the primary efficacy endpoint in the study or may potentially impact the interpretation of safety. Major protocol deviations may include, but are not limited to the following:

- Randomized subjects who do not meet the inclusion criteria
- Randomized subjects who meet any of the exclusion criteria
- Subjects who received the wrong treatment
- Concomitant use of prohibited medications
- Randomized subjects who met withdrawal criteria during the study but were not withdrawn
- Subjects whose IP was interrupted 14 consecutive days or more during the double-blind treatment period OR had IP compliance less than 80% from Weeks 8-12
- Subjects who were not compliant in study procedures (e.g., if 3 or more days of diary entry were missed between visits that were a 2-week period or if 6 or more days of diary entry missed between visits that were a 4-week period)

4. GENERAL STATISTICAL CONSIDERATIONS

4.1. General Principles for Data Analysis

4.1.1. Multicenter Study

In this study the stratified permuted block randomization is not done within centers. The analyses will be conducted by pooling data from all study centers and will not include study center as a covariate in the statistical modeling.

4.1.2. Testing Strategy and Multiplicity Adjustments

No formal multiplicity adjustment will be performed. All efficacy analyses will be considered descriptive. Ninety-percent confidence intervals will be provided for each treatment group and nominal p-values from comparisons to placebo may be provided for descriptive purposes as a measure of the strength of the association between the endpoint and the treatment effect.

4.1.3. Examination of Subgroups

To determine whether the treatment effect is consistent across various subgroups, the primary efficacy endpoint will be summarized descriptively for each of the following subgroups:

- Baseline abdominal pain intensity score (<6 vs \geq 6)
- Age category (<40, \geq 40 to <65, \geq 65 years)
- Race (as CRF page)
- Randomized prior to 31Dec2019 vs Randomized after 31Dec2019
- Baseline Bristol Stool Scale (< 5.5 vs \geq 5.5)

Note, the protocol amendment in Nov2019 changed the fecal calprotectin testing to optional and that it should only be considered if there is a strong suspicion in the opinion of the investigator that the subject has inflammatory bowel disease (IBD) (e.g., family history in a 1st degree relative). In order to allow time operationally for sites to implement this a date of 31Dec2019 was chosen as the cutoff.

All efficacy data including eDiary and ePRO data will be summarized by IBS sub-type (IBS-D and IBS-M) and all IBS.

